7.1.2. QTcF Stopping Criteria

Subjects must permanently discontinue IP for QTcF >500 msec.

7.1.3. Liver Function: Actions and Follow-up Assessments

Liver chemistry will be evaluated as specified in the SoA (Section [1.3.1](#) – PCP and Section [1.3.2](#) – OLE).

For ALT or AST $\geq 3 \times$ ULN, refer to [Appendix 7](#) for guidelines on monitoring and criteria for possible dose modifications (Section [6.5.1](#)) and temporary interruption of IP with possible restarting criteria and actions.

Any occurrence of a confirmed ALT or AST value $\geq 3 \times$ ULN will be monitored and evaluated for an etiology (for example viral hepatitis, drug and herbal supplements, environmental exposure, alcohol use, and other) in consultation with the Sponsor ([Appendix 2](#), [Table 5](#)).

7.1.4. Pregnancy

A subject must permanently discontinue IP if she becomes pregnant. See [Appendix 4](#) and Section [8.3.5](#) for additional details.

See the SoA (Section [1.3.1](#) – PCP and Section [1.3.2](#) – OLE) for data to be collected at the time of IP discontinuation (Early Withdrawal from Study visit in PCP and EOT visit for OLE) and follow-up and for any further evaluations that need to be completed.

7.1.5. Introduction of New UC Therapy Stopping Criteria

A subject requiring introduction of a new therapy to treat UC between 2 weeks prior to the screening flexible sigmoidoscopy/colonoscopy and the PCP Week 36 visit must permanently discontinue IP.

7.2. Lost to Follow-up

A subject will be considered lost to follow-up if he or she repeatedly fails to engage for scheduled visits and is unable to be contacted by the study site.

The following actions must be taken if a subject fails to return to the clinic for a required study visit (for exceptions refer to [Appendix 9](#)):

- The site must attempt to contact the subject and reschedule the missed visit as soon as possible and counsel the subject on the importance of maintaining the assigned visit schedule and ascertain whether or not the subject wishes to and/or should continue in the study.
- Before a subject is deemed lost to follow-up, the Investigator or designee must make every effort to regain contact with the subject (where possible, 3 telephone calls and, if necessary, a certified letter to the subject's last known mailing address or local equivalent methods). These contact attempts should be documented in the subject's medical record.
- Should the subject continue to be unreachable, he/she will be considered to have withdrawn from the study.

Discontinuation of specific sites or of the study as a whole are handled as part of [Appendix 1](#).

8. STUDY ASSESSMENTS AND PROCEDURES

Study procedures and their timing are summarized in the SoA (Section [1.3.1](#) – PCP and Section [1.3.2](#) – OLE). Protocol waivers or exemptions are not allowed.

- Immediate safety concerns should be discussed with the Sponsor's Medical Monitor (or designee) immediately upon occurrence or awareness to determine if the subject should continue or discontinue IP.
- Adherence to the study design requirements, including those specified in the SoA, is essential and required for study conduct.
- All screening evaluations must be completed and reviewed to confirm that potential subjects meet all eligibility criteria. The Investigator will maintain a screening log to record details of all subjects screened and to confirm eligibility or record reasons for screening failure, as applicable.
- In case of natural disasters or pandemics, some visits/study procedures may be done via virtual visits or at home visits. Refer to [Appendix 9](#) and Study Reference Manuals for more details.

8.1. Efficacy Assessments

8.1.1. Clinical, Endoscopic and Histologic Assessment

Throughout the study, subjects will capture Stool frequency and Rectal bleeding symptoms on a daily basis in an eDiary. For evaluation of eligibility, the Rectal bleeding and Stool frequency subscores of the Mayo score will each be calculated based on the average of the most recent 3 days with non-missing data within 14 days prior to the PCP Day 1/Week 0, excluding the day of and the day after flexible sigmoidoscopy/colonoscopy and the day(s) of bowel preparation, if performed. Subjects bowel preparation for flexible sigmoidoscopy/colonoscopy should follow standard clinical practice. Subjects will be instructed that a stool is defined as a trip to the toilet when the subject has either a bowel movement, or passes blood alone, blood and mucus, or mucus only.

Screening, PCP Week 12, and PCP Week 36 (and at an Unscheduled UC Disease Activity Criteria Assessment visit(s) and the Early Withdrawal from Study visit, if applicable) endoscopic subscores will be assessed by both a central reader (who is blinded to treatment assignment, visit, and subject symptoms) and local endoscopist (who is blinded to treatment assignment). The same local endoscopist assesses the endoscopic subscore for a particular subject throughout the study, if possible. Differences between the local endoscopist and the central reader will be adjudicated by a second blinded central reader as described in the Imaging Charter. Centrally read endoscopic subscores will be used for both eligibility determination and efficacy analyses. Histologic scores (eg, RHI) will be evaluated by a blinded central reader.

Flexible sigmoidoscopy/colonoscopy and histology assessments will consist of assessing the Endoscopic subscore of the sigmoid colon at approximately 15 to 25 cm from the anal verge. Six biopsies will be obtained during the endoscopic procedures from the area that appears to be most affected by UC in this sigmoid colon segment.

Biopsies may also be evaluated for PK, gene expression, and immunohistochemistry signals of biological activity.

8.1.2. Mayo Score and Modified Mayo Score

Mayo score is used for inclusion into the study rather than a Modified Mayo score (used to evaluate efficacy) given the limited information available at the study inception regarding Modified Mayo score cut points that define a mild-to-moderate patient population.

The Mayo score is a conventional assessment of UC disease activity and is commonly used in clinical studies of UC. The score is composed of four subscores, each ranging from 0 to 3, that are summed to give a total score ranging from 0 to 12 points, with higher scores indicating greater severity (Adapted from [Schroeder, 1987](#)):

1. Stool frequency:

0 = Normal number of stools for this subject

1 = 1 to 2 stools more than normal

2 = 3 to 4 stools more than normal

3 = 5 or more stools than normal

Each subject serves as his or her own control to establish the degree of abnormality of the stool frequency. The control value is the number of stools in a 24-hour period when the subject was in remission from UC, or, if the subject does not report having previously achieved remission from UC, the number of stools the subject reports per day before initial onset of signs and symptoms of UC.

2. Rectal bleeding:

- 0 = No blood seen
- 1 = Streaks of blood with stool less than half the time
- 2 = Obvious blood with stool most of the time
- 3 = Blood alone passes

The daily bleeding score represents the most severe bleeding of the day.

3. Findings on endoscopy:

- 0 = Normal or inactive disease
- 1 = Mild disease (erythema, decreased vascular pattern)
- 2 = Moderate disease (marked erythema, absent vascular pattern, friability, erosions)
- 3 = Severe disease (spontaneous bleeding, ulceration)

4. Physician's Global Assessment

- 0 = Normal
- 1 = Mild disease
- 2 = Moderate disease
- 3 = Severe disease

The PGA acknowledges the three other criteria, the subject's recollection of abdominal discomfort and general sense of wellbeing, and other observations, such as physical findings and the subject's performance status. It is recommended that the same physician performs the PGA for a particular subject throughout the study.

The Modified Mayo score is an endpoint measure composed of: Stool frequency, Rectal bleeding, and Endoscopic subscores (where the Endoscopic subscore value of 1 does not include friability), each ranging from 0 to 3, that are summed to give a total score ranging from 0 to 9 points, with higher scores indicating greater severity.

The Partial Mayo score is an endpoint measure composed of: Stool frequency, Rectal bleeding, and PGA subscores, each ranging from 0 to 3, that are summed to give a total score ranging from 0 to 9 points, with higher scores indicating greater severity.

The 6-point Mayo score is an endpoint measure composed of: Stool frequency and Rectal bleeding subscores, each ranging from 0 to 3, that are summed to give a total score ranging from 0 to 6 points, with higher scores indicating greater severity.

8.1.3. Robarts Histopathology Index (RHI) Score, Geboes Score and Ulcerative Colitis Index-100

The RHI is a validated instrument that measures histological disease activity in UC. The RHI consists of 4 items: chronic inflammatory infiltrate, lamina propria neutrophils, neutrophils in epithelium, and erosion or ulceration. The RHI score ranges from 0-33 and is derived from Geboes score ([Mosli, 2017](#)).

$$\begin{aligned} \text{RHI} = & 1 \times \text{chronic inflammatory infiltrate level (4 levels)} \\ & + 2 \times \text{lamina propria neutrophils (4 levels)} \\ & + 3 \times \text{neutrophils in epithelium (4 levels)} \\ & + 5 \times \text{erosion or ulceration (4 levels after combining Geboes 5.1 and 5.2)} \end{aligned}$$

The Geboes score is divided into 6 grades: architectural changes [grade 0], chronic inflammatory infiltrate [grade 1], lamina propria eosinophils and neutrophils [grade 2A and 2B], neutrophils in epithelium [grade 3], crypt destruction [grade 4] and erosions or ulcerations [grade 5]. The Geboes score is calculated as the highest grade with a corresponding subgrade score > 0, excluding Geboes Grade 2A, and ranges from 0 to 5.

The Ulcerative Colitis Index-100 (UC-100) score is the composite index ($1 + 16 \times$ Stool frequency subscore [0 to 3] + 6 x Endoscopic subscore [0 to 3] + 1 x RHI score [0 to 33]) ([Jairath, 2019](#)).

8.2. Safety Assessments

8.2.1. Physical Examinations

A complete physical examination will be performed at timepoints designated in the SoA (Section [1.3.1](#) – PCP and Section [1.3.2](#) – OLE) and will include:

- General appearance/inspection
- Skin
- Neck
- Lymphatic
- Respiratory
- Cardiovascular
- Abdominal system
- HEENT (head, eyes, ears, nose, throat)
- Other- for those body systems, not listed above considered necessary per PI's discretion

A symptom-directed physical examination will be conducted if clinically indicated throughout the study. Investigators should pay special attention to clinical signs related to previous serious illnesses.

8.2.2. **Vital Signs**

- Heart rate, respiratory rate, temperature and blood pressure will be assessed.
- Blood pressure and pulse measurements will be assessed with the subject in a sitting position with a completely automated device. Manual techniques will be used only if an automated device is not available or if the automated cuff sizes available are not large enough for the subject's arm circumference.
- Vital signs will be measured after 5 minutes rest and prior to ECG measurements on days where the 12-lead ECG will be obtained.
- Height and weight will also be measured and recorded. Height will only be recorded at Screening.

8.2.3. **Electrocardiograms**

- 12-lead ECGs will be obtained at timepoints specified in the SoA (Section 1.3.1 – PCP and Section 1.3.2 – OLE) using an ECG machine that automatically calculates the heart rate and measures PR, QRS, QT, and QTc intervals.
- Subjects with evidence of a significant abnormality in the 12-lead ECGs obtained at screening, including prolongation of the QTc interval, will not be eligible to randomize into the study.
- ECG will be centrally read by the Sponsor's designee via the electronic portal.
- Original paper tracings and tracing copies of the ECGs should be stored in the source documents.

8.2.4. **Clinical Safety Laboratory Assessments**

- See [Appendix 2](#) for the list of clinical laboratory tests to be performed and the SoA (Section 1.3.1 – PCP and Section 1.3.2 – OLE) for the timing and frequency. Details for collection, processing, and shipping of samples to the central laboratory are provided in a separate Central Laboratory Manual.
- The Investigator must review and document review of the laboratory report. The Investigator must record any clinically relevant changes occurring during the study in the AE section of the eCRF. The laboratory reports must be filed with the source documents.
- All laboratory tests with values considered clinically significant during participation in the study should be repeated as medically indicated until the values return to normal or baseline or are no longer considered clinically significant by the Investigator or Sponsor's Medical Monitor (or designee).
 - If such values do not return to normal/baseline within a period of time judged reasonable by the Investigator, the etiology should be identified, and the Sponsor notified.

- All protocol-required laboratory assessments, as defined in [Appendix 2](#), must be conducted in accordance with the Central Laboratory Manual and the SoA (Section [1.3.1](#) – PCP and Section [1.3.2](#) – OLE).

8.3. Adverse Events and Serious Adverse Events

The definitions of an AE and SAE can be found in [Appendix 3](#).

AEs will be reported by the subject (or, when appropriate, by a caregiver, surrogate, or the subject's legally authorized representative).

The Investigator and any qualified designees are responsible for detecting, documenting, and recording events that meet the definition of an AE or SAE. The Investigator and qualified designees remain responsible for following AEs that are serious, considered related to the IP or study procedures, or that caused the subject to discontinue from IP or from the study (see Section [7.1](#)).

8.3.1. Time Period and Frequency for Collecting AE and SAE Information

AEs and SAEs will be collected beginning at the time of consent through the end of the follow-up period (including PCP and OLE). All medical occurrences, with the exception of SAEs, that begin after obtaining ICF and before first dose of IP will be recorded on the Medical History section of the eCRF and not the AE section.

All SAEs will be recorded and reported to the Sponsor or designee immediately upon the site learning of an event and under no circumstance should this exceed 24 hours, as indicated in [Appendix 3](#). The Investigator will submit any updated SAE data to the Sponsor within 24 hours of it being available.

Investigators are not obligated to actively seek AEs or SAEs after conclusion of the study participation. However, if the Investigator learns of any SAE, including a death, at any time after a subject has been discharged from the study, and he/she considers the event to be reasonably related to the IP or study participation, the Investigator must promptly notify the Sponsor.

8.3.2. Method of Detecting AEs and SAEs

The method of recording, evaluating, and assessing causality of AE and SAE and the procedures for completing and transmitting SAE reports are provided in [Appendix 3](#).

Care will be taken not to introduce bias when detecting AEs and/or SAEs. Open-ended and non-leading verbal questioning of the subject is the preferred method to inquire about AE occurrences.

8.3.3. Follow-up of AEs and SAEs

After the initial AE/SAE report, the Investigator is required to proactively follow each subject at subsequent visits/contacts. All SAEs will be followed until resolution, stabilization, the event is otherwise explained, or the subject is lost to follow-up (as defined in Section [7.2](#)). Further information on follow-up procedures is given in [Appendix 3](#).

8.3.4. Regulatory Reporting Requirements for SAEs

- Prompt notification by the Investigator to the Sponsor of an SAE is essential so that legal obligations and ethical responsibilities towards the safety of subjects and the safety of an IP under clinical investigation are met.
- The Sponsor has a legal responsibility to notify both the local regulatory authority and other regulatory agencies about the safety of an IP under clinical investigation. The Sponsor will comply with country-specific regulatory requirements relating to safety reporting to the regulatory authority, IRB/IEC, and investigators.
- Investigator Safety Reports must be prepared for suspected unexpected serious adverse reactions (SUSAR) according to local regulatory requirements and Sponsor policy, and then the reports will be forwarded to Investigators as necessary.
- An Investigator who receives an Investigator Safety Report describing an SAE or other specific safety information (eg, summary or listing of SAEs) from the Sponsor will review and then file it along with the IB and will notify the IRB/IEC, if appropriate according to local requirements.

8.3.5. Pregnancy

- Details of all pregnancies in female subjects and female partners of male subjects will be collected after the start of study IP and until birth.
- If a pregnancy is reported, the Investigator should inform the Sponsor within 24 hours of learning of the pregnancy and should follow the procedures outlined in [Appendix 4](#).
- Abnormal pregnancy outcomes (eg, spontaneous abortion, fetal death, stillbirth, congenital anomalies, ectopic pregnancy) are considered SAEs.

8.3.6. Disease-Related Events and/or Disease-Related Outcomes Not Qualifying as AEs or SAEs

Worsening of UC will be evaluated by efficacy assessments (Section 8.1) and is a disease-related outcome not qualifying as an AE unless the Investigator considers the worsening UC to have met the definition of an SAE ([Appendix 3](#)). Worsening UC meeting the definition of an SAE will be reported in the appropriate eCRF. Worsening UC not meeting the definition of an SAE should not be reported as an AE. Worsening UC will be evaluated by efficacy endpoints and by the occurrence of SAEs, and will be monitored by the Sponsor on a routine basis.

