- Anti-nuclear antibody
- Anti-smooth muscle antibody
- Type 1 anti-liver kidney microsomal antibodies
- Quantitative total immunoglobulin G (IgG) or gamma globulins
- Serum acetaminophen assay
- Serum creatine phosphokinase (CPK)
- Lactate dehydrogenase (LDH)
- Complete Blood Count with differential
- Obtain blood sample for pharmacokinetic (PK) analysis

The above assessments will be conducted only if required.

APPENDIX 3. ADVERSE EVENTS: DEFINITIONS AND PROCEDURES FOR RECORDING, EVALUATING, FOLLOW-UP, AND REPORTING

Definition of AE

AE Definition

• An adverse event, AE, is any untoward medical occurrence in a subject or clinical study subject whether or not considered related to the IP.• NOTE: An AE can therefore be any unfavorable and unintended sign (including an abnormal laboratory finding), symptom, or disease (new or exacerbated) temporally associated with the use of IP.

Events Meeting the AE Definition

• Any abnormal laboratory test results (hematology, clinical chemistry, or urinalysis) or other safety assessments (eg, ECG, radiological scans, vital signs measurements), including those that worsen from baseline, considered clinically significant in the medical and scientific judgment of the Investigator (ie, not related to progression of underlying disease).• Exacerbation of a chronic or intermittent pre-existing condition including either an increase in frequency and/or intensity of the condition.• New conditions detected or diagnosed after IP administration even though it may have been present before the start of the study.• Signs, symptoms, or the clinical sequelae of a suspected drug-drug interaction.• Signs, symptoms, or the clinical sequelae of a suspected overdose of either IP or a concomitant medication. Overdose per se will not be reported as an AE/SAE unless it is an intentional overdose taken with possible suicidal/self-harming intent. Such overdoses should be reported regardless of sequelae.• “Lack of efficacy” or “failure of expected pharmacological action” per se will not be reported as an AE or SAE. Such instances will be captured in the efficacy assessments. However, the signs, symptoms, and/or clinical sequelae resulting from lack of efficacy will be reported as SAE if they fulfil the definition of an SAE.

Events NOT Meeting the AE Definition

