- Medical or surgical procedure (eg, endoscopy, appendectomy): the condition that leads to the procedure is the AE.
- Situations in which an untoward medical occurrence did not occur (social and/or convenience admission to a hospital).
- Anticipated day-to-day fluctuations of pre-existing disease(s) or condition(s) present or detected at the start of the study that do not worsen.
- Fluctuations in UC disease activity that do not worsen compared to a subject's medical history of UC

Definition of SAE

If an event is not an AE per definition above, then it cannot be an SAE even if serious conditions are met (eg, hospitalization for signs/symptoms of the disease under study, death due to progression of disease).

An SAE is defined as any untoward medical occurrence that, at any dose:**Results in death****Is life-threatening**

The term 'life-threatening' in the definition of 'serious' refers to an event in which the subject was at risk of death at the time of the event. It does not refer to an event, which hypothetically might have caused death, if it were more severe.

Requires inpatient hospitalization or prolongation of existing hospitalization

In general, hospitalization signifies that the subject has been detained (usually involving at least an overnight stay) at the hospital or emergency ward for observation and/or treatment that would not have been appropriate in the physician's office or outpatient setting. Complications that occur during hospitalization are AEs. If a complication prolongs hospitalization or fulfills any other serious criteria, the event is serious. When in doubt as to whether "hospitalization" occurred or was necessary, the AE should be considered serious.

Hospitalization for elective treatment of a pre-existing condition that did not worsen from baseline is not considered an AE.

Results in persistent disability/incapacity

- The term disability means a substantial disruption of a person's ability to conduct normal life functions.
- This definition is not intended to include experiences of relatively minor medical significance such as uncomplicated headache, nausea, vomiting, diarrhea, influenza, and accidental trauma (eg, sprained ankle) which may interfere with or prevent everyday life functions but do not constitute a substantial disruption.

Is a congenital anomaly/birth defect**Other situations:**

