In general, whenever a tabular summary of AEs is mentioned in this SAP, it is intended that the tabular summary is in reference to treatment emergent AEs, even though “treatment emergent” may not be explicitly mentioned. By-subject data listings of AEs will include all events regardless of treatment emergence.

Counting will be at the subject level for each level of summarization (eg, any AE, SOC, and PT), with subjects experiencing more than one AE counted only once. For summary of AEs by severity, subjects will be counted once at the highest severity reported at each level of summarization. AEs that are missing severity will be presented in summary tables as “Missing”. AEs that are missing relationship to study treatment will be presented in summary tables as “Related”.

The following AE summaries will be presented:

- Overall Summary of AEs, showing the number and percentage of subjects with an AE; a moderate or severe AE; a severe AE; a serious adverse event (SAE) including UC SAEs (defined as the PT of ‘Colitis ulcerative’); an SAE excluding UC SAEs; a treatment-related AE; a treatment-related SAE; an AE leading to dose reduction, dose interruption, or discontinuation of PCP study treatment; an AE leading to dose reduction; an AE leading to dose interruption; an AE leading to discontinuation of PCP study treatment; an AE leading to withdrawal from PCP; and an AE resulting in death.
- Incidence of AEs by SOC and PT
- Incidence of AEs by PT

- Incidence of AEs $\geq 5\%$ in Any Treatment Group by PT
- Incidence of AEs $\geq 2\%$ Higher in Either GB004 Treatment Group Relative to Placebo by PT
- Incidence of SAEs by SOC and PT including UC SAEs
- Incidence of SAEs by SOC and PT excluding UC SAEs
- Incidence of AEs by SOC, PT, and maximum severity
- Incidence of Treatment-Related AEs by SOC and PT
- Incidence of AEs Leading to Dose Reduction of PCP Study Treatment by SOC and PT
- Incidence of AEs leading to Dose Reduction of PCP Study Treatment by PT
- Incidence of AEs Leading to Dose Interruption of PCP Study Treatment by SOC and PT
- Incidence of AEs Leading to Dose Interruption of PCP Study Treatment by PT
- Incidence of AEs Leading to Discontinuation of PCP Study Treatment by SOC and PT
- Incidence of AEs Leading to Discontinuation of PCP Study Treatment by PT
- Incidence of AEs Leading to Withdrawal from PCP by SOC and PT
- Incidence of AEs Leading to Withdrawal from PCP by PT
- Incidence of AEs Resulting in Death by SOC and PT

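### Protocol 8.3.6 keeps non-serious UC worsening out of AE reporting, Appendix 3 implies the opposite for flares beyond the subject's history, and the SAP counts whatever sites enter

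*Protocol*

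**What the plan says.** Protocol 8.3.6 is the section written for worsening of the study disease. It calls such worsening a "disease-related outcome not qualifying as an AE unless the Investigator considers the worsening UC to have met the definition of an SAE" and then adds: "Worsening UC not meeting the definition of an SAE should not be reported as an AE".

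Protocol 8.3 points elsewhere for the definition itself: "The definitions of an AE and SAE can be found in" Appendix 3. Five statements in that appendix bear on the question:

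- The general definition covers any "symptom, or disease (new or exacerbated) temporally associated with the use of IP".
- The list of events that meet the definition includes "Exacerbation of a chronic or intermittent pre-existing condition including either an increase in frequency and/or intensity of the condition". No exception is made for UC.
- The list of events that do not meet it includes "Fluctuations in UC disease activity that do not worsen compared to a subject's medical history of UC".
- The lack-of-efficacy bullet leaves lack of efficacy as such to the efficacy assessments. It asks for reporting of the clinical consequences only when they are serious.
- The SAE definition opens by saying that anything outside the AE definition is barred from being an SAE even when a seriousness condition is met. One of its examples is admission to hospital for the study disease.

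SAP 9.1 decides treatment emergence by start date. It separates UC events, identified by the preferred term Colitis ulcerative, only among serious events, for example in the table "Incidence of SAEs by SOC and PT excluding UC SAEs". The overall, by-preferred-term and discontinuation AE summaries have no such split.

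**The concern.** A site that works from Appendix 3, as Section 8.3 directs, can reasonably enter a non-serious flare as an AE. A site that works from 8.3.6 will not. Both are following the protocol.

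TEAE incidence is the named safety endpoint of the placebo-controlled period and the primary endpoint of the open-label extension. UC worsening is also what the efficacy endpoints measure. Mixed reporting would therefore carry an efficacy outcome into the safety endpoint in an unknown share of sites, and any difference in disease control between arms would appear as a difference in tolerability.

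Serious flares raise a separate problem. Under the opening sentence of the SAE definition, a site could conclude that they are not reportable as SAEs at all, although 8.3.6 and the SAP expect them to be.

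**Working it through.** The plan states no figure on this point, so there is none to reproduce. The check is a comparison of texts, followed by an illustration of size.

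**Three cases against the text**

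1. *Non-serious flare within the subject's usual UC history.* 8.3.6 says not to report it. The UC bullet of Appendix 3 also excludes it. The two agree.
2. *Non-serious flare worse than the subject's history.* 8.3.6 says not to report it. In Appendix 3, the general definition and the exacerbation bullet both take it in, and the UC bullet does not take it out, because that bullet reaches only fluctuations that do not worsen. The lack-of-efficacy bullet would keep it out, but only if the investigator sees the flare as lack of efficacy. That bullet does not name UC. The outcome depends on the page read.
3. *Flare requiring hospital admission.* Under 8.3.6 the worsening becomes an AE if it meets the SAE definition. Under Appendix 3 it can be an SAE only if it is already an AE. Read together the two are circular, and the hospital-admission example points to not reporting. The SAP nevertheless plans SAE tables with and without UC events, so it expects these events in the data.

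No sentence in 8.3, 8.3.6 or Appendix 3 states which passage takes precedence.

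**Illustration of size (assumed rates)**

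Let b be the incidence of other TEAEs, w the incidence of non-serious UC worsening beyond history, and s the share of those events entered as AEs. Assume worsening and other TEAEs are independent, and b and s are the same in each arm.

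- TEAE incidence = b + (1 − b) × s × w
- Between-arm shift = (1 − b) × s × (difference in w between arms)

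The documents give no value for w. The only nearby figure for b is from the 7-day healthy-volunteer study in Protocol 2.3.2 (28% on GB004, 30% on placebo), which is a weak guide to patients treated for 12 or 36 weeks. All inputs below are therefore assumptions.

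All events entered (s = 1):

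- b = 45%, w = 25% on placebo and 15% on GB004: 0.45 + 0.55 × 0.25 = 58.75%, and 0.45 + 0.55 × 0.15 = 53.25%. The shift is 5.5 points.
- b = 30%, w = 20% on placebo and 10% on GB004: 0.30 + 0.70 × 0.20 = 44%, and 0.30 + 0.70 × 0.10 = 37%. The shift is 7 points.
- With the worsening rates exchanged between arms, each shift keeps its size and changes sign.

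Under 8.3.6 (s = 0) the between-arm difference is zero in all of these scenarios.

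A quarter of events entered (s = 0.25):

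- b = 45%: 0.55 × 0.25 × 10 points = 1.4 points.
- b = 30%: 0.70 × 0.25 × 10 points = 1.75 points.

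For scale, 5.5 points is 0.055 × 65 = 3.6 subjects per arm. The standard error of that difference with 65 per arm is √[(0.5875 × 0.4125 + 0.5325 × 0.4675) / 65] = 8.7 points.

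**The case against.** The strongest reply is that 8.3.6 is the dedicated, explicit rule, that it cross-refers to Appendix 3, and that a specific rule is naturally read as an exception to a general definition. The lack-of-efficacy bullet supports this from inside the appendix. So does the SAP: splitting out UC events only among SAEs is what one would plan if UC worsening were expected in the AE data only when serious. Stray non-serious entries would still be visible in the by-preferred-term tables and the subject listings, and SAP 9.1 allows in-depth summaries of particular AEs. TEAE incidence is summarised descriptively, so no test depends on it.

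Much of this stands. A reader might infer that Appendix 3 flatly declares non-serious UC worsening to be an AE. It does not. The result follows from a general bullet combined with the limit on an exclusion, it covers only worsening beyond the subject's history, and another bullet points the other way.

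The reply does not remove the problem, because Appendix 3 has a UC-specific bullet of its own. If all non-serious worsening were already excluded, that bullet's restriction to fluctuations that do not worsen would do no work. Nor does the reply deal with the SAE sentence. Visibility in a by-term table does not supply an overall TEAE incidence without these events.

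**Conclusion.** The protocol contains an unresolved inconsistency, and the SAP has no step that neutralises it. It affects non-serious flares beyond the subject's history and, through the SAE sentence, serious flares as well. It should be corrected, but it does not touch the primary efficacy analysis.

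Size and direction cannot be derived from the documents. With other TEAEs at 30% to 45%, worsening at 10% to 25% per arm, and a 10-point difference in worsening between arms, the shift is about 5.5 to 7 points either way if all such events are entered. It is about 1.4 to 1.75 points if a quarter are.

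Two stronger readings are tempting and are not supported:

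- *That the ambiguity makes GB004 look safer.* This presumes more worsening on placebo, which is a hypothesis of the trial. If worsening were commoner on GB004, the shift would go against it.
- *That AEs leading to discontinuation are distorted.* Protocol 7.1 lists lack of efficacy and adverse event as separate reasons, so stopping for a flare has a route that is not an AE. Some misallocation is possible where a site has entered the flare as an AE, but the documents do not show that it occurs.

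**What to change.** **Protocol, or a site memo.** State that 8.3.6 governs worsening of UC, and align Appendix 3 with it in one edit:

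- Refer the exacerbation, UC-fluctuation and lack-of-efficacy bullets to 8.3.6, so that non-serious worsening is handled in one way.
- Amend the opening sentence of the SAE definition and its hospital-admission example, so that serious UC worsening clearly remains reportable as an SAE.

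These changes belong together. Removing UC from the exacerbation bullet while leaving the SAE sentence untouched would strengthen the reading that serious flares cannot be SAEs.

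**SAP 9.1.** Present the overall, by-preferred-term and AE-leading-to-discontinuation summaries with and without Colitis ulcerative, as is already planned for SAEs. This also deals with events already entered.

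The cost is a short clarification and a few repeat tables.
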